7.0 Study Withdrawal/Discontinuation

Subject withdraws, and adverse events will be reviewed by the Safety Officer, PI, Program Officer and study team members at the semi-annual meeting, or as prescribed in the Data Safety and Monitoring plan.

8.0 Statistical Considerations

The proposed study is a RCT comparing the multi-component, supportive care intervention (IN-PEACE) to usual care. Primary and secondary outcomes will be collected at baseline, 3, 6, 9, 12, 15, 18, 21, and 24 months. A patient reaches study endpoint by either completing 24 months of follow-up or other conditions described in Subject tracking. We will compare baseline characteristics between the intervention group and the control group using two sample *t*-tests for continuous normally distributed variables, Wilcoxon test for continuous non-normal variables, or chi-square tests for categorical variables. Variables found to be significantly different at the α =0.05 level will be adjusted in the comparisons of all outcome variables.

Table 4: Power estimates for significant interactions between group and time in the mixed effect

models with 85 patients per group.

Outcome Measures	. Ou	d Change in tcome th interval)	Power			
	Intervention	Intervention Usual Care				
Aim 1: NPI-Q Severity	-0.45	0.2	80%			
Aim 2: SM-EOLD	1.31	0*	85%			
Aim 3a: Caregiver NPI-Q distress	-0.39	0.08	80%			
Aim 3b: Caregiver PHQ-9	-0.22	0.16	81%			

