2.0 Rationale and Specific Aims

Aim 1: To test the effect of the IN-PEACE intervention on patients' neuropsychiatric symptoms (e.g., agitation/aggression, anxiety, repetitive behaviors). Mixed effects models will be used to compare repeated NPI-Q scores obtained at 3, 6, 9, 12, 15, 18, 21, and 24 months. Repeatedly measured NPI-Q scores will be the dependent variable in the model.

Aim 2: To test the effect of the IN-PEACE intervention on patients' overall symptom outcomes. Analyses in this aim will use repeatedly measured SM-EOLD scores over 24 months of follow-up as the dependent variable in the mixed effects model, similarly to the approach described for Aim 1.

Aim 3: To test the effect of the IN-PEACE intervention on caregivers' distress and mood. Aim 3 analyses will use repeatedly measured caregiver NPI-Q distress scores and caregiver PHQ-9 over 24 months of follow-up as the dependent variables in separate mixed effects models, similar to the approach for Aim 1.

Aim 4: Evaluate the effect of the IN-PEACE intervention on ER/hospital use. ER/hospitalization events will be obtained from accessing electronic medical records maintained by the Indiana Health Information Exchange (IHIE) and the Indiana Network for Patient Care (INPC). Poisson regression models will be used to compare rates of any ER/hospitalization event between the two groups while adjusting for dementia severity and significant baseline variables that differ between the two groups.

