4.0 Enrollment/Randomization

After enrollment and baseline assessments are completed, subjects will be classified according to disease severity (moderately severe (FAST = 5) or severe (FAST = 6-7).

Stratified randomization based upon dementia severity will be used to assign patient-caregiver dyads to either the intervention or usual care arm.

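### Covariates for Aims 1-3 are chosen by baseline significance tests, while the baseline outcome score and the FAST stratum are not pre-specified

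*Combined protocol and SAP*

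**What the plan says.** **Covariate rule (section 8.0).** Arms are compared at baseline by t-test, Wilcoxon or chi-square test. The rule follows: "Variables found to be significantly different at the" 0.05 "level will be adjusted in the comparisons of all outcome variables".

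**Models (section 2.0).** Aim 1 uses mixed effects models to "compare repeated NPI-Q scores obtained at 3, 6, 9, 12, 15, 18, 21, and 24 months". Aim 2 proceeds "similarly to the approach described for Aim 1", and Aim 3 likewise refers back to Aim 1. No covariate is named for these three aims. Aim 4 alone names one, comparing event rates "while adjusting for dementia severity and significant baseline variables that differ between the two groups".

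**Design (section 4.0).** "Stratified randomization based upon dementia severity will be used to assign patient-caregiver dyads to either the intervention or usual care arm". The strata are FAST 5 and FAST 6-7.

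**Baseline data (section 8.0).** "Primary and secondary outcomes will be collected at baseline, 3, 6, 9, 12, 15, 18, 21, and 24 months". The plan does not say whether the month-0 score is a response, a covariate or unused.

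**Powered test (Table 4).** The table is headed "Power estimates for significant interactions between group and time in the mixed effect" models, with 85 patients per group. The wording of Aim 1 does not mention an interaction.

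**The concern.** A baseline test in a randomised trial asks whether chance produced a difference. It does not ask whether the variable predicts the outcome. The best predictor of a follow-up score is usually the same score at baseline, and this rule admits it only when the arms happen to differ on it at p<0.05. Three things are at stake.

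1. **Precision.** If the arms are compared on follow-up level, the variance that baseline could explain stays in the error term in about 95% of trials.
2. **Conditional bias.** An imbalance just short of p<0.05 is left in place and carries into the follow-up difference.
3. **Pre-specification.** The covariate set is unknown until arm-level data are examined, and it then applies to every outcome whether or not it is relevant to that outcome.

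The stratum raises a related point. Randomisation uses FAST, so the analysis would normally include it. Balance by design means a significance rule will not bring it in.

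**Working it through.** **Inputs from the plan.** Selection threshold 0.05; 85 per group for power and 112 randomised per arm; follow-up at eight visits (months 3-24); Table 4 powers of 80-85%. The plan gives no SD, correlation or variance component, so those below are assumptions.

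**1. The plan's own figure.** The 80% for Aim 1 in Table 4 (change of -0.45 against 0.2 per interval, a difference of 0.65) cannot be reproduced without an SD. Solving backwards with a two-sided 0.05 test (sidedness assumed): SD = 0.65 × √(85/2) / (1.960 + 0.842) = 1.51 per interval. This does not show whether baseline was used.

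**2. How often the rule acts.** A continuous baseline score is flagged in about 5% of trials. The largest unflagged difference is 1.96 × √(2/n): 0.30 SD at 85 per arm and 0.26 SD at 112. For FAST, simulated permuted blocks of 4, 6 or 8 within strata, with a FAST 5 share of 30%, 50% or 70%, gave p<0.05 in 0 of 2,000 trials in each of the nine settings. Blocking is assumed; without it the figure would be about 5%.

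**3. Comparison of level.** Let r be the baseline-outcome correlation. Always adjusting multiplies the variance by 1 - r². For an effect with 80% unadjusted power, adjusted power is Φ(2.802/√(1 - r²) - 1.960). At r = 0.5 this is Φ(2.802/0.866 - 1.960) = Φ(1.275) = 90%. The rule itself was simulated with 40,000 trials per setting, 85 per arm and a standardised effect of 0.432:

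| | r = 0.4 | r = 0.5 | r = 0.6 |
|---|---|---|---|
| Power, rule | 80.4% | 81.4% | 81.4% |
| Power, baseline always adjusted | 86.1% | 89.9% | 93.7% |
| Overall null size, rule | 4.6% | 4.2% | 4.0% |
| Null size when baseline p is 0.05-0.20, rule | 7.8% | 8.4% | 9.7% |
| Same band, always adjusted | 5.3% | 4.9% | 4.8% |

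Normal-theory integration agrees: power under the rule 81%, 81%, 82%; overall size 4.6%, 4.3%, 4.0%; band rate 7.6%, 8.9%, 10.3%.

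**4. Are these correlations plausible?** For the mean of eight visits with equal correlation ρ between visits, the variance is (1 + 7ρ)/8 and the correlation of baseline with that mean is ρ/√((1 + 7ρ)/8). At ρ = 0.3 this is 0.3/√0.3875 = 0.48; at ρ = 0.5 it is 0.5/√0.5625 = 0.67. Moderate visit-level correlations therefore reach or exceed the upper part of the range in the table.

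**5. Imbalance just under the threshold.** Given a baseline z of 1.96, the unadjusted statistic has mean 1.96r and variance 1 - r². Its false-positive rate is close to 1 - Φ(1.96(1 - r)/√(1 - r²)). At r = 0.5 this is 1 - Φ(1.13) = 13%. For the eight-visit mean it is 12%, 19% and 27% at ρ = 0.3, 0.5 and 0.7.

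**6. Group-by-time slope.** Twelve illustrative sets were used: intercept SD 2-3, slope SD 0.3-0.5 per visit, residual SD 2-3, intercept-slope correlation -0.3, 0 or 0.3. With months 3-24 as responses, baseline explains 0-3% of slope variance. Power is about 80% unadjusted and 80-81% with baseline-by-time adjustment. The null rate in the same p-value band is 4.6-6.0%. A baseline main effect alone leaves the slope variance unchanged (factor 1.00).

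**7. Month 0 as a response.** For the same twelve sets, assuming that the effect grows linearly from month 0, the generalised least squares variance gives 83-86% power with free arm means at month 0 and 83-94% with equal arm means, against 80% from months 3-24 only.

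**The case against.** The strongest reply is that Table 4 powers the interaction, and for that test steps 3 and 5 do not apply. This is correct, and the concern is limited accordingly. It does not remove the level reading: Aim 1 is worded as a comparison of repeated scores, and nothing outside Table 4 names the interaction.

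Second, the rule is fixed in advance and uses baseline data only, so it gives no freedom to choose covariates after seeing outcomes. That also stands. The complaint is an unknown and poorly chosen covariate set, not outcome-driven selection.

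Third, the 8-10% applies to about 15% of trials and is offset elsewhere. With 5% error where adjustment occurs, the remaining 80% of trials run at (0.046 - 0.05 × 0.05 - 0.15 × 0.078)/0.80 = 4.0% for r = 0.4, and by the same arithmetic at 3.4% and 2.9% for r = 0.5 and 0.6. On average the rule is slightly conservative.

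Fourth, section 8.0 does not say that nothing else will be adjusted, and month 0 may be intended as a response. If so, baseline information is already used and the first two harms largely fall away. But Aim 1 lists months 3-24 only, and severity is named for Aim 4 alone, so the text does not support assuming it.

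Finally, the stratum result depends on blocking, the cost of omitting FAST has not been quantified, and no calculation was made for the Poisson model. A balanced stratum left out mainly costs precision. The Aim 4 change rests on the same reasoning, not on a figure.

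**Conclusion.** The concern holds and should be fixed. The text is clear on the selection rule and silent on the baseline score and stratum for Aims 1-3. Overall type I error is not at risk.

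If level is the primary contrast, the rule gives up about 6, 9 and 12 percentage points of power at correlations of 0.4, 0.5 and 0.6 (86.1 - 80.4, 89.9 - 81.4, 93.7 - 81.4). It also leaves conditional false-positive rates of 8-10% when the baseline p-value is 0.05-0.20. If the interaction is primary, both effects are small. What remains is a covariate set that is not known in advance and an unstated use of month 0, which can move power from 80% to 83-94% in the settings examined.

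Confidence is high on the text and on the direction of the effects. The sizes depend on assumed correlations and variance components, complete data for the slope, and linear growth of the effect for the month-0 figures.

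**What to change.** 1. In section 8.0, delete the sentence that starts "Variables found to be significantly different at the". In Aim 4, keep dementia severity and drop the adjustment for variables found to differ at baseline.
2. State the primary contrast for Aims 1-3: the arm difference in level (at a named month or averaged over visits) or the group-by-time interaction.
3. Add: *Every Aim 1-3 model includes the baseline value of that outcome and the FAST stratum (5 versus 6-7), whatever the baseline p-values.* Say whether baseline is a covariate or a month-0 response with equal arm means. If the interaction is primary, note that a baseline main effect alone does little for it.
4. Report baseline characteristics descriptively, without using tests to select covariates.

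The cost is a few sentences in sections 2.0 and 8.0. Baseline scores and FAST stage are already collected at month 0.

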9.0 Privacy/Confidentiality Issues

We will also take great care in assuring data security. Perhaps the most important element of data security is proper training of the scientists and their staff in research involving human subjects and in privacy and confidentiality. Data are handled only by research staff with specific training in data privacy and confidentiality. Data are stored on a secured workstation that is in a locked office within a locked suite of offices and the workstation and files are password protected. On rare occasions when data are to be transferred from secured workstations to one of the investigators' workstations for further analyses, the transferred dataset will be stripped of unique identifiers (deidentified dataset) including SSN, name, address, dates, and any personal identifiers. This is standard operating procedures for our work with research data. In addition, Regenstrief Institute databases and individual workstations are protected from unauthorized remote access by a sophisticated firewall which is tested on a regular basis. Data presented in reports are always reported in aggregate and never contain personally identifiable health information.

10.0 Follow-up and Record Retention

The study is scheduled for 24 months. Records will be maintained in secure location and will be retained as required per regulations.
